6.4 Missing Diagnosis Dates

If the month and year are present but the day is missing, the diagnosis date will be set to first day of the relevant month. If only the year is recorded the diagnosis date will be set as “01-Jan” for that year.

6.5 Missing Safety Data

A treatment-related TEAE is defined as a TEAE that is assessed by the Investigator or Sponsor as being related to study drug. If a TEAE has a missing relationship to study drug it is assumed to be related to the study drug for analysis purposes.

A disease-related TEAE is defined as a TEAE that is assessed by the Investigator or Sponsor as being related to the disease under study. If a TEAE has a missing relationship to the disease under study it is assumed to be related to the disease under study for analysis purposes unless the TEAE is assessed by the investigator as treatment-related.

Missing severity assessments will be summarised as severe.

7.0 STATISTICAL ANALYSIS

All statistical analyses and reporting will be performed using the SAS® System Version 9.4 or later.

Unless otherwise specified, continuous variables will be summarized with descriptive statistics (n, mean, median, standard deviation, standard error, minimum, and maximum), and categorical variables will be summarized with counts and percentages.

7.1 Calculation of Study Day:

Study day will be calculated as the number of days from first dose of study drug (Day 1):

- Date of event – date of first dose of study drug + 1, for events on or after first dose
- Date of event – date of first dose of study drug, for events before first dose

To this end, Day 0 remains undefined.

Definition of Baseline:

Study day will be calculated as the number of days from first dose of IP/study drug (Day 1). Baseline measurements will be the last measurement for the corresponding variable prior to the first randomized dose on Day 1.

Out of Window and Unscheduled Visits:

The protocol defined windows for scheduled visits will not be used in the analyses by visit. Data will be assigned to the scheduled visit closer in time to the actual visit. Unscheduled visit data will only be used in an analysis if there are no other available data closer in time to a scheduled visit. All unscheduled visit data will be included in data listings.

7.2 Subject Disposition

Subject disposition, including the number of subjects randomized, treated, and completing the study (and completing each study visit), will be tabulated by treatment group. The percentage of subjects treated and completing the study will be based on the total number randomized. A subject data listing will be provided.

Eligibility criteria exemptions and major protocol deviations will be summarized by treatment group and presented in a listing. Major protocol deviations may include the following: violation of inclusion or exclusion criteria, using prohibited medications, non-adherence to study treatment schedule, and unblinding of the masked assessor at day 1 study drug dosing. A guideline for classification of patients as belonging to the per protocol analysis dataset will be documented prior to database unmasking as will the masked review of patient data for purposes of classification.

The total number and percentage of subjects included in each of the analysis datasets will be summarized by treatment group, with percentages based on the total number of randomized subjects. A subject data listing will be provided.

Discontinuations and the reasons for discontinuation from study medication will be summarized for all randomized subjects. Summaries will include the number and percentage of subjects within each treatment group. Reasons for Discontinuation or Early Termination/Study Withdrawal following the receipt of study drug will include the following:

- Intolerable Adverse Event
- Death
- Lost to Follow Up
- Physician Decision
- Prohibited Medication Required
- Pregnancy
- Protocol Noncompliance
- Site Terminated By Sponsor
- Study Terminated By Sponsor
- Withdrawal of Consent
- Lack of Efficacy
- OTHER: specify

A subject data listing will be provided.

7.3 Demographic and Baseline Characteristics

Subject demographic and baseline characteristics will be summarized for the ITT analysis population; however, should there be a reasonable difference in the size of the ITT and safety analysis populations, demographic and baseline characteristics will be summarized for both. The comparability of groups used in comparison analyses will be characterized in tables of demographic data. Summary tables will be supported with individual subject data listings.

Continuous variables such as age will be summarized using descriptive statistics (n, mean, standard deviation, median, minimum, and maximum), and categorical variables such as gender, race, ethnicity, will be summarized using counts and percentages of subjects.

7.4 Treatment Compliance and Exposure

The duration of drug exposure and % compliance will be summarized by treatment group.

Duration of drug exposure will be calculated for each subject as the last date of dosing minus the first date of dosing + 1. The number and percentage of subjects by treatment group will be summarized according to the following duration-of-exposure categories: '< 1 wk', '1 to < 3 wks', '3 to < 5 wks' and '≥ 5 wks.'

A subject data listing will be provided.

7.5 Study Endpoints

7.5.1 Primary Endpoint

The primary endpoint is the change from baseline to 1-minute post-instillation of IP in Drop Discomfort VAS score at Visit 2. The baseline measure will be taken 1-minute following Refresh Plus® administration at least 2 hours prior to IP administration.

7.5.2 Key Secondary/Efficacy Endpoints

- Change from baseline in Drop Discomfort VAS score (both eyes assessed together)
 - Summarized and analyzed for change from baseline to 1-minute and 5-minute post instillation, for the AM and PM doses on Visits 2 (randomization), 3, 4 and 5 (15 analyses in addition to the primary endpoint). An overall analysis of all discomfort scores will be undertaken
- Change from baseline in each of the 6 Individual Symptom Severity Assessments (VAS) (both eyes assessed together)
 - Summarized and analyzed for change from baseline to visit 3, 4 and 5. An overall analysis for each VAS incorporating all visits will be undertaken
- Change from baseline of the sum of the Individual Symptom Severity Assessments (VAS Total Symptom Summary Score) (both eyes assessed together)
 - Summarized and analyzed for change from baseline to visit 3, 4 and 5. An overall analysis incorporating all visits will be undertaken
- Change from baseline in SANDE score (both eyes assessed together)
 - Summarized and analyzed for change from baseline to visit 3, 4 and 5. An overall analysis incorporating all visits will be undertaken
- Change in unanesthetized STT score (each eye assessed individually)
 - Summarized and analyzed for change from baseline to visit 4 and 5
- Change from baseline in FCS total score (NEI/Industry Workshop 0-15 scale) Safety Endpoints (each eye assessed individually)
 - Summarized and analyzed for change from baseline to visit 3, 4 and 5. An overall analysis incorporating all visits will be undertaken

7.5.3 Safety Endpoints

- Treatment-emergent adverse events (TEAEs)
- Change from screening in BCVA (each eye assessed individually)
- Changes from baseline in Slit-Lamp Biomicroscopy (each eye assessed individually)
- Changes from screening in Dilated Ophthalmoscopy (each eye assessed individually)

7.5.4 Exploratory Endpoints

Four additional composite endpoints have been defined as exploratory endpoints. These endpoints will be assessed for each subject in their eye that achieves the worst STT score at baseline. Should a subject have identical STT scores in both eyes at baseline, the eye with the worst FCS score will be used. Should these scores also be equal, the right eye will be used.

- Proportion of patients achieving an improvement from baseline in the STT of ≥ 5 mm at visits 4 and 5
- Proportion of patients achieving an improvement from baseline in the STT of ≥ 10 mm at visits 4 and 5
- Proportion of patients achieving an improvement from baseline in the STT of ≥ 5 mm along with any improvement in FCS total score at visits 4 and 5
- Proportion of patients achieving an improvement from baseline in the STT of ≥ 10 mm along with any improvement in FCS total score at visits 4 and 5

7.6 Methods of Analysis

7.6.1 Ordinal and Continuous Variables

All endpoints, other than TEAE, slit-lamp biomicroscopy and ophthalmoscopy, are measured on a VAS or ordinal scale and will be summarized and analyzed as continuous data.

Summaries of scores (absolute and change from baseline) by treatment group will be displayed for each assessment time (where applicable) at each visit. Treatment comparisons will be made using a t-test from an ANCOVA model including terms for treatment group, investigator site and baseline score. Results will be summarized by the estimate of treatment difference, a 95% CI for the treatment difference and a p-value. If assumptions are violated, the Wilcoxon rank sum test will be used. If required, transformations may be considered in order to meet the necessary assumptions.

For variables assessed at multiple time points and/or multiple visits the individual analyses will be complemented by an overall supplementary analysis incorporating all data collected for the endpoint in question. Endpoints will be analyzed using a Mixed Effect Model Repeated Measures

(MMRM) analysis with treatment group, visit, treatment-by-visit interaction, baseline score and investigator site included as covariates in the model. Results will be expressed as differences between treatment groups (along with the associated 95% CI). Least Square (LS) means and corresponding 95% CIs for the change in baseline values will be presented for each visit. Where endpoints are collected multiple times within a visit additional covariates will be added to the model. E.g. time post dose (1 minute / 5 minutes) and AM or PM assessment. The model will be fitted using an unstructured covariance matrix. Should this model fail to converge, an autoregressive covariance matrix will be used. The covariance matrix used will be referenced in table footnotes. The Kenward-Roger degree of freedom adjustment will be applied. In order to aid the modelling process it is possible that smaller centers will need to be combined. If necessary, the smallest center will be combined with the next smallest, and so on.

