1.1.1 Limitations of Current Treatment

Current therapy includes a stepped approach which starts with over-the-counter (OTC) lubricants and artificial tear replacements, and then expands to include topical anti-inflammatory therapy and punctal occlusion [1]. There are currently two FDA-approved prescription medications used for DED, topical cyclosporine (Restasis[®]) [6] and lifitigrast (Xiidra[®]) [7]. A significant number of patients using Restasis[®] experience the following problems: ocular irritation upon instillation, slow onset of response, and limited efficacy (Restasis[®] Package Insert, see [Appendix 8](#)). Problems with Xiidra[®] include instillation irritation, dysgeusia and reduced visual acuity which occurred in 5-25% of subjects in clinical trials (Xiidra[®] Package Insert [7]). There is a clear unmet clinical need for improved therapeutic options for patients with moderate to severe DED.

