an AE, it is the Investigator's responsibility to acquire sufficient information in order to assess causality. This may require additional laboratory testing, physical examinations, telephone contacts, etc. In circumstances where the Investigator is unable to contact with the subject, the Investigator must provide a written statement to Aurinia confirming that the subject is lost to follow-up.

In order to avoid bias in eliciting AEs, subjects should be asked a non-leading question, such as "How are you feeling?". It is also important to question the subject in a non-leading way about changes in their health or concomitant medication usage since their last visit. This information should be collected prior to completion of assessments at all study visits (with the exception of the SANDE and Individual Symptom Assessment VAS). In addition, any symptoms/conditions reported during assessments and deemed to be clinically significant by the Investigator will be considered AEs.

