10.6.3 Safety Analysis

Adverse events will be aggregated by System Organ Class and preferred term and presented as summary tables. Other safety endpoints will be summarized by visit as absolute values and changes from baseline (as appropriate). Endpoints with specific ranges will have counts of values falling outside of the range summarized by visit and overall.

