6.1 Clinical Trials Experience

Because clinical trials are conducted under widely varying conditions, adverse reaction rates observed in the clinical trials of a drug cannot be directly compared to rates in the clinical trials of another drug and may not reflect the rates observed in practice.

In clinical trials, the most common adverse reaction following the use of **RESTASIS**[®] was ocular burning (17%).

Other reactions reported in 1% to 5% of patients included conjunctival hyperemia, discharge, epiphora, eye pain, foreign body sensation, pruritus, stinging, and visual disturbance (most often blurring).

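### The readable SAP methods treat BCVA solely as per-eye continuous data, with no loss threshold or count of subjects who lost vision; a descriptive count table should be added once the reference visit is reconciled

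*SAP*

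**What the plan says.** **Analysis type.** SAP 7.6.1 states: "All endpoints, other than TEAE, slit-lamp biomicroscopy and ophthalmoscopy, are measured on a VAS or ordinal scale and will be summarized and analyzed as continuous". BCVA is a listed safety endpoint, worded in SAP 7.5.3 as "Change from screening in BCVA (each eye assessed individually", and is not among the three exceptions. It therefore falls under the ANCOVA (treatment, site, baseline score), and under the MMRM because it is measured at several visits. SAP 7.6.1 also provides a fallback: "If assumptions are violated, the Wilcoxon rank sum test will be used".

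**Descriptive statistics.** SAP 7.0 says that "continuous variables will be summarized with descriptive statistics (n, mean, median, standard deviation, standard error, minimum, and maximum". The summary is therefore wider than a mean.

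**Categorical safety summaries.** SAP 7.6.3 sends only TEAEs, slit-lamp and ophthalmoscopy findings to Section 8. There, slit-lamp and ophthalmoscopy get frequency tables, shift tables and listings, and pregnancy tests get a listing. BCVA has no subsection. The method for proportions (SAP 7.6.2) adjusts for baseline Schirmer score and serves the Schirmer and staining endpoints of SAP 7.5.4.

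**Protocol rule on counts.** Protocol 10.6.3 says: "Endpoints with specific ranges will have counts of values falling outside of the range summarized by visit and overall". No range is set for BCVA or its change, and the SAP methods do not repeat the rule.

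**Adverse event route.** Protocol 9.3.1 says that "any symptoms/conditions reported during assessments and deemed to be clinically significant by the Investigator will be considered AEs".

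**The concern.** Loss of acuity happens in individual eyes of individual subjects. The question a safety reader asks is how many subjects lost a meaningful amount of vision, in which arm, and whether they recovered. A mean, a model-based difference or a rank test does not answer it. Nor can two per-eye tables be added together: if k right eyes and k left eyes show a loss, the number of subjects affected lies anywhere from k to 2k.

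Assessing safety is part of the secondary objective (Protocol 3.2). If a few subjects lost acuity, the BCVA section of the report could show a mean difference near zero with a non-significant p-value, which is easily misread as showing no effect on vision.

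**Working it through.** **Inputs from the documents.** About 45 subjects per arm (Protocol 5.1). One letter is worth 0.02 logMAR, and a higher logMAR is worse (Protocol Appendix 6). Neither document gives a figure for BCVA variability or for a loss that matters.

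**Assumptions.** Losses of 0.2 and 0.3 logMAR (10 and 15 letters at 0.02 each) are used for illustration. The background SD of BCVA change is taken as 0.06 to 0.15 logMAR.

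**The plan's own figure.** The only sample size in the plan is for drop discomfort. For a 15 mm difference, SD 20 mm, two-sided 5% and 90% power, n = 2 × (1.960 + 1.282)² × (20/15)² = 37.4, so 38 per group. Power at 38 is 90.5% by the normal formula and 89.7% by the t distribution. Allowing for 15% dropout, 76/0.85 = 89.4, so 90 randomized and 45 per arm. The arm size reproduces, but it was not chosen with BCVA in mind.

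**Shift in an arm's mean for one eye.** Shift = k × loss / 45, where k subjects lose acuity in that eye and the others do not change.

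| k of 45 | Percent | Loss 0.2: shift (letters) | Loss 0.3: shift (letters) |
|---|---|---|---|
| 1 | 2.2% | 0.004 (0.2) | 0.007 (0.3) |
| 3 | 6.7% | 0.013 (0.7) | 0.020 (1.0) |
| 4 | 8.9% | 0.018 (0.9) | 0.027 (1.3) |

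Small gains elsewhere can cancel the shift: four losses of 0.3 and twelve gains of 0.1 give (4 × 0.3 − 12 × 0.1)/45 = 0.

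**Chance that a comparison of means detects it.** Take 4 of 45 losing 0.3 in one arm and none in the other. The difference is 0.027. The affected arm's variance is SD² + p(1 − p) × 0.3², with p = 4/45. A two-sample t-test at two-sided 5% has about 31% power at background SD 0.06, 19% at 0.10 and 12% at 0.15. This is an unadjusted test, so the planned ANCOVA could do somewhat better.

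**What the other planned statistics show.** The maximum change shows the single worst eye at each visit. It does not show whether one subject or four were affected, or whether it was the same subject each time. The median hardly moves when three or four of 45 values shift in the tail. The SD would rise, but it gives no count.

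**What a count would show.** 4/45 = 8.9% (exact 95% CI 2.5% to 21.2%). With 0/45 the upper 95% limit is 7.9%. The chance of seeing at least one case in 45 is 1 − (1 − p)⁴⁵, which is 36% at a true rate of 1% and 90% at 5%. Against 0/45, a count of 4/45 gives Fisher p = 0.12, so the table is descriptive.

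**Reference value.** SAP 7.5.3 measures BCVA change from screening. Protocol 8.1.3.1 uses Visit 1 for eligibility and Visit 2 as baseline. SAP 7.1 defines baseline as the last value before the first randomized dose, which by the schedule is Visit 2. SAP Section 9 does not list a change of BCVA reference among the changes from the protocol.

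**The case against.** Four stronger readings are tempting, and the documents do not support them.

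- **That BCVA is analyzed only as a mean.** A reader might infer this from the ANCOVA and MMRM. SAP 7.0 adds median, minimum and maximum, and SAP 7.6.1 has a rank-test fallback. A single large loss would be visible as the maximum.
- **That a loss in a few subjects would go unreported.** Findings that the Investigator judges clinically significant become adverse events. SAP 8.1 counts TEAEs by subject, merges two-eye events and lists them. This is a real subject-level route. Its limit is that it depends on judgment with no acuity threshold, so it may differ between sites and does not capture every loss of a given size.
- **That reduced acuity is a documented risk of a study treatment.** Protocol 1.1.1 mentions "dysgeusia and reduced visual acuity which occurred in 5-25% of subjects in clinical trials", but for Xiidra, which is not given in this trial, and the percentage range covers a group of problems. The Restasis insert (Protocol Appendix 8, 6.1) lists "pruritus, stinging, and visual disturbance (most often blurring" among reactions seen in 1% to 5%. That concerns the comparator only, and is a reported reaction rather than measured acuity. Neither passage concerns VOS.
- **That no categorical BCVA table exists.** The SAP table list is redacted, so this cannot be known. Protocol 10.6.3 is also not declared withdrawn; it simply has no BCVA range to act on.

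Two further points on the other side stand. At Visits 3 to 5 the morning dose is withheld and BCVA is listed before the clinic dose, and Visit 6 comes at least three days after treatment ends. Brief blur at instillation would therefore largely escape any BCVA table and would appear, if anywhere, as an adverse event. In addition, the counts will be small, and no primary or key secondary conclusion depends on them.

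**Conclusion.** The point holds in a limited form. The readable methods give per-eye continuous summaries and models for BCVA, and nothing that states how many subjects lost vision by a defined amount. Three of 45 subjects losing 0.30 logMAR in an eye would appear as a one-letter shift in that eye's arm mean. The maximum and the adverse event tables narrow the gap but do not close it. The size of the shift follows from the arm size and the letter value in the documents; the loss thresholds and the SD range are assumptions. The omission does not show that either product harms acuity, and it does not affect the primary result. It is an inexpensive improvement to the safety reporting. The conflict over the reference visit is separate and definite, and it affects the planned continuous analysis as well.

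**What to change.** 1. Reconcile the BCVA reference value across SAP 7.5.3, SAP 7.1 and Protocol 8.1.3.1 before unmasking. Two of the three point to Visit 2. If screening is kept, record it in SAP Section 9 as a change from the protocol.
2. Add a BCVA subsection to SAP Section 8. On the Safety Set, by arm, give the number and percent of subjects whose logMAR worsened from the reference value by at least each prespecified threshold in either eye. The thresholds could be, for example, 0.2 and 0.3, for the sponsor to confirm. Show this at each post-dose visit, at the worst post-dose value and at the last available visit, with exact 95% confidence intervals. Count each subject once, and state the denominator (subjects with a reference and a post-dose value in the same eye).
3. List the subjects who meet a threshold, with both eyes at all visits, so that persistence can be seen.
4. Keep the continuous summary. Whether to keep its p-value is a reporting preference.

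If the redacted table list already contains such a table, only its thresholds, two-eye rule and reference visit need to be written into the methods.

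The cost is one table and one listing from BCVA already collected at Visits 1 to 6, with no new procedure. The downside is that the counts will be small and can only be read descriptively.

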7.6.2 Endpoints measured as a Proportions

The proportion of subjects achieving the endpoint will be summarized at each visit. Results of the proportional endpoints will be expressed as an odds ratio and an associated 2-sided confidence interval for voclosporin compared to Restasis®. The logistic model used will include terms for treatment group, baseline STT score and investigator site. Odds ratios greater than unity will mean the odds of achieving the endpoint are greater for voclosporin than for Restasis® and therefor indicate a benefit of voclosporin. The p-value for the treatment difference will also be reported.

7.6.3 Other Variables

For TEAEs, slit-lamp biomicroscopy and ophthalmoscopy findings, see Safety Evaluations below.

8.0 SAFETY EVALUATIONS

8.1 Adverse Events

For screen failure subjects, any AEs and SAEs occurring during the screening period (after informed consent) will be recorded in the subject's source documentation only and will not be collected on the eCRF.

For enrolled subjects, all AEs and SAEs will be recorded in the AE section of the subject's eCRF and source documentation.

A treatment emergent adverse event (TEAE) is defined as any AE that has an onset on or after the first dose of IP/study drug and on or before the last dose of IP/study drug plus 3 days. Only treatment-emergent events will be summarized. All events in the clinical database regardless of when they occurred will be provided in data listings i.e., for enrolled subjects, data listings will have screening AEs/SAEs and TEAEs/serious TEAEs. Adverse events will be presented by Medical Dictionary of Regulatory Activities (MedDRA) primary system organ class (SOC) and preferred term (PT).

An overall summary will be presented which gives the number and percentage of subjects within each treatment group (n (%)), and the number of events (E) that experienced:

- Any TEAE
- Any Treatment-Related TEAE
- Any Disease-Related TEAE
- Any Serious TEAE
- Any Serious Treatment-Related TEAE
- Any Serious Disease-Related TEAE.
- Any TEAE Leading to Study Drug Discontinuation
- Any Treatment-Related TEAE Leading to Study Drug Discontinuation
- Any Disease-Related TEAE Leading to Study Drug Discontinuation
- Any TEAE with Outcome of Death
- Any Treatment-Related TEAE with Outcome of Death
- Any Disease-Related TEAE with Outcome of Death

In summary tables, ocular AEs recorded once for each eye separately but in the same timeframe will be summarized once at the greater intensity and relationship to study drug. The number and percentage of subjects experiencing one or more events within a MedDRA SOC and PT class without regard to intensity, relationship, or seriousness will be tabulated by treatment group. Additional tables for TEAEs and Serious TEAEs will display events by SOC, PT, and maximum intensity.

The following Adverse Event listings will be provided:

- Listing of TEAEs by treatment group ordered by subject, SOC, PT, and date (study day)
- Listing of serious TEAEs by treatment group ordered by subject, SOC, PT, and onset date (study day)
- Listing of TEAEs leading to study drug interruption or discontinuation
- Listing of TEAEs resulting in death
- Listing of all AEs not classified as Treatment Emergent

